After surgery, as in Aim 1, a trained CRC will visit patients daily or as needed while hospitalized. Control group patients will complete a daily application-generated usage report (date, time, duration); VR-BF patients will have this information, along with HRV and respiratory rate data, obtained from the device. To help determine what outcomes may be impacted by VR-BF for future trial development, patients will also be asked to document pain and anxiety scores before and after each VR-BF or application session using the NRS.^{110,111} Patients will self-report and document these scores before each session and then immediately, 15 minutes, and 30 minutes after session completion. All pain scores and opioid consumption (in morphine equivalents mg/kg/day) will be collected from EPIC, the electronic medical record, for each 24-hour period during study enrollment; anxiety scores are not documented by the nursing staff so only self-reported scores will be used. Documented pain scores will also help finalize the “dose” of VR-BF to be used in the efficacy trial as we will assess for correlation, if any, between pain score and use of VR-BF. At the final study visit prior to discharge, patients will answer a questionnaire and engage in a semi-structured interview soliciting qualitative feedback about their experience with the intervention or control to finalize the study protocol for the clinical efficacy trial. Participants will be given the option to take the VR-BF platform home or continue using the *Manage My Pain* application for up to two weeks after discharge. If this option is selected, patients will complete a daily log/report documenting use, pain scores, and opioid consumption. During the first postoperative clinic visit, VR-BF and reports/logs will be collected and questions about home use will be asked, answered, and recorded. Parents will also be asked to complete a survey about their experience and opinions. If patients cannot be met during the first postoperative clinic visits, other arrangements will be made to collect the information and equipment.

Feasibility and Acceptability of Technology-Based Interventions in the Perioperative Setting

Data Collection (Table 3). **Feasibility.** *Recruitment:* The number of patients screened per month will be recorded and assessed for eligibility; reasons for ineligibility will be recorded. If 80% of patients do not meet criteria, we will adjust criteria as necessary. *Enrollment and randomization:* Enrollment and randomization will be defined as agreeing to participate in the study and being willing to be randomized. We will record the number of eligible patients approached and enrolled each month. We will collect reasons for refusal to enroll, including unwillingness to be randomized. If rates are not maintained at 80%, we will adjust strategies accordingly. *Retention:* We will define retention as the number of patients who complete the study by participation in the last study visit for both arms. We will collect reasons for dropout. If $\geq 80\%$ retention is not maintained, we will evaluate reasons for dropout. *Adherence:* We will define adherence to preoperative training as completion of the education and training session with the study team and completion of $\geq 5/7$ daily sessions. Adherence to postoperative VR-BF/app use will be defined as completion of $\geq 5/7$ daily sessions. Our target will be $\geq 80\%$ completion. We will collect reasons for failure.

Questionnaires and the semi-structured interview will also assess feasibility using measures based in the literature.¹¹⁹

Acceptability. Treatment/Study

Burden: Burden will be assessed by collecting data on daily log completion, data from questionnaires, and participation in the interview. We will collect reasons for drop out to better understand treatment and study burden.

	Measures	Definition	Benchmarks	Additional Data
Feasibility	Recruitment	Number of patients screened per month	$\geq 80\%$ will meet eligibility criteria	Reasons for not meeting criteria
	Enrollment and randomization	Number of patients approached who agree to enroll in the study and be randomized to a treatment arm	$\geq 80\%$ of those approached will agree to enroll and be randomized	Reasons for refusal, including unwillingness to be randomized
	Retention	Number of participants who complete the study as defined by participation in the last study visit	$\geq 80\%$ retention	Reasons for dropout
	Adherence	Treatment-specific adherence	$\geq 80\%$ will complete ≥ 1 session per day for $\geq 5/7$ days (preop) and ≥ 1 session per day (postop)	Reasons for failure
Acceptability	Burden	Percent completion of daily logs/reports, percent completion of questionnaires and interview	$\geq 80\%$ completion of all study measures	Reasons for failures
	Satisfaction	Patient/parent satisfaction	NA	Questionnaires, semi-structured interview
	Credibility	Perception of efficacy	NA	Questionnaires, semi-structured interview
	Tolerability	Number and percent of patients experiencing AEs	$< 1\%$ will experience a serious AE	Reasons for not tolerating therapy, AEs

Table 3. Feasibility and acceptability outcome measures and benchmarks.

We anticipate $\geq 75\%$ of patients will complete all study measures, with completion of daily logs defined as completion of $\geq 5/7$ daily logs. **Satisfaction:** Satisfaction will be assessed by questionnaire and the semi-structured interview. Development of these qualitative assessments are based on reported measures of acceptability.^{102,119} **Treatment credibility:** We will define treatment credibility as patient perception of treatment efficacy as measured by survey and interview. **Tolerability:** We will record the number of adverse effects (minor, moderate/severe)

Feasibility and Acceptability of Technology-Based Interventions in the Perioperative Setting

from therapy. We anticipate a very low rate (<1%) of adverse events. We will collect qualitative acceptability data using questionnaires and the semi-structured interview using measures based in the literature.^{102,119}

Additional Data Collection

The following data may be collected in the CRF: (a) type and duration of anesthesia and surgery where applicable; (b) anxiety and pain scores (both intensity and unpleasantness as well as pain medications used to treat the patient (including doses and number of rescues); (c) satisfaction with VR device/comments; (d) desire for study team to return; (e) any critical or adverse events. Survey data will be captured directly into REDCap or paper forms.

We will also collect descriptive data from the health record for each patient, such as age, sex, race, ethnicity, ASA status, type of surgery, diagnosis at surgery, underlying medical conditions, medications taken prior to surgery, and treatment history. We will record VR experience, presentation order, and any use of corrective lenses. Anxiety and pain will be collected with numerical rating scale (NRS) prior to and after the VR intervention for patients in all 3 cohorts. Additional outcome measures will be pulled from EPIC regarding narcotic/medication consumption during hospitalization, all pain assessments during the hospitalization, and length of stay. We will collect all heart rate, respiratory rate, and FOREVR VR usage from the FOREVR VR device (or HeartMath if necessary).

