Study population. Subjects will be recruited when scheduled for surgery at Nationwide Children's Hospital. We will coordinate recruitment efforts with surgeons who perform surgeries that require pain management by the Acute Pain Service. We will screen patient lists provided by the surgical schedulers as well as operating room schedules to identify potentially eligible patients prior to their scheduled surgery. Messages assessing interest in the study will be sent through MyChart. We anticipate recruiting 1 patient per week. We are confident that we can successfully recruit and enroll our full cohort of up to 102 patients: up to 32 for Aim 1 (minimum 12 patients) and 70 for Aim 2.

Blinding. Although patients will not be blinded to the intervention they receive, patients and families will be blinded with respect to the study arms. Therefore, the consent will describe the study as assessing technology-based interventions for the management of pain without specific detail about VR-BF (FOREVR VR) or *Manage My Pain* or indicate the use of any device, such as a headset. Once assigned to a group, patients will receive a handout describing the intervention with instructions and information about what participation entails. We will also blind data collection by using a study number for each patient and will not indicate in which arm the patient is enrolled in data collection forms. The biostatistician will be blinded to the patient groups during analysis.

Study Materials

Self-reported measures. Patients will be asked to complete a survey at the end of study participation as well as participate in a semi-structured interview. Parents will also be asked to complete a survey. The questionnaires will be completed through the Research Electronic Data Capture (REDCap) database.

Feasibility and Acceptability of Technology-Based Interventions in the Perioperative Setting

VR headset. Participants will use the Oculus/Meta Quest VR headset with the FOREVR VR device. When necessary, we will use the software supplied by Invincikids (*Mindful Aurora* application) with the Oculus/Meta Quest.

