Requirements. A signed consent form will be obtained from the participant. For participants who cannot consent for themselves, such as those below the legal age, a parent, legal guardian, or person with power of attorney, must sign the consent form; additionally, the participant's assent must also be obtained if he or she is able to understand the nature, significance, and risks/benefits associated with the study. The consent form will describe the purpose of the study, the procedures to be followed, and the risks and benefits of participation. A copy of the signed consent form will be given to the participant, parent, or legal guardian, and this fact will be documented in the participant's record.

Procedure. The approved, HIPAA compliant informed consent/assent will be provided to the study participant and the parents for review. The consent will be completed through the Research Electronic Data Capture (REDCap) database or on paper forms (if eConsent is unavailable at the time of consent). After allowing adequate time for review, the participant and parents will have the opportunity to ask questions and receive answers. When all questions have been answered, the consent and/or assent will be signed, and a signed copy will be provided to the participant and parents. This will all be conducted before any study measures interventions are undertaken.

Phone Consent. Due to needing subjects to begin study participation prior to surgery, we are requesting permission to consent by phone in order to have time to have subjects be trained on the technology prior to the scheduled surgery. Potential subjects may schedule surgery over the phone or at an in-person visit however subjects who are in person may not be available for approach due time constraints or already being overwhelmed with information regarding the surgery.

Documentation of Ineligibility. Screen failures will be documented on the source worksheets with the supporting data accompanying the eligibility screening form. Documentation of ineligibility or non-participation for each consented participant will be maintained in an electronic database (e.g., REDCap). Reports detailing the reasons for screen-failure and non-participation of eligible participants will be reviewed by the study team to determine if the exclusion criteria require revision in order to make the study accessible to families and study participants.

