15.0 Risks to Subjects*

There are minimal physical risks to participants and enrollment in this study will not alter their management. All patients will receive pain management per the Acute Pain Service during the duration of the study.

Clinical Care. Enrolled patients will receive the same care and attention in the postoperative period or during their hospital stay as those non-enrolled patients. Patients will be given the opportunity to end participation in the study at any time.

VR Headset. VR headsets used in this study are minimal risk devices, and because they are considered a relaxation device by the FDA, they are not regulated. Risks specific to this research study are minimal or absent with the greatest risk being motion sickness while the headset is in place¹¹³ and a theoretical risk of inducing seizures (0.025% in pediatric data supplied by a similar Samsung device). Should motion sickness occur, the participant will be instructed to remove the device to ensure resolution of symptoms; we will exclude patients with a history of seizure disorder or other relevant neurological conditions. Other adverse events will be defined using standard criteria. The researchers shall monitor the patient while the device is applied. Serious adverse events, although unanticipated, will be reported using routine avenues. The Starlight Xperience device was used in our pilot study (**CCHMC IRB #2018-2892**) without any documentation of adverse effects. We have since purchased new headsets, the Oculus Quest and Oculus Quest 2, which have been used in prior studies without any reported adverse events (**CCHMC IRBs #2019-1090, 2020-0258, 2020-0612**). We will continue updating to newer versions of the Oculus/Meta Quest as they become available when new equipment is required.

FOREVR VR. This device has been approved for both research and clinical use by the Equipment and Standards Committee at Cincinnati Children's Hospital. It is a noninvasive device to measure respiratory rate (via chest movement) and heart rate using an ear clip. This device is also considered a minimal risk device. This is the first study to use FOREVR VR.

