22.0 Consent Process

Children will be identified from the operating room schedule and surgery patient lists. Parents and children will be provided with oral and written information about the research project and a signed consent will be obtained from the participant. For participants who cannot consent for themselves, such as those below the legal age, a parent or legal guardian must sign the consent form; additionally, the participant's assent will also be obtained if he or she is able to understand the nature, significance and risks/benefits associated with the study. The consent form will describe the purpose of the study, the procedures to be followed, and the risks/benefits of participation. A copy of the signed consent form (including assent where appropriate) will be given to the participant, parent or legal guardian and a copy will be placed in the patient's medical record. Patients will be contacted prior to surgery and told about the study. If interested, consent may be signed electronically (see below) or may be obtained during the first preoperative study visit.

Participants may choose to complete an electronic consent by using an application (e.g., REDCap) supported by Nationwide Children's Hospital in compliance with HIPAA designed to protect PHI in the electronic transfer and storage of the consent form. Participants that choose to complete the electronic consent will have the opportunity to review the consent form and talk with research staff. If the potential participant agrees to participate, they will have an opportunity to check a box stating that they agree to provide their consent / parental permission / assent. There will also be fields for their typed name and their signature, along with witness fields. Once the electronic form has been submitted, a copy of the signed form will be provided to the participant. Electronic consents will be maintained within the application. In the event electronic consent is not available paper consent forms will be used.

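### The consent is to mention no device, yet must describe procedures and risks that belong to the headset; the instructions need reconciling, and refusals after disclosure need a counting rule

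*Combined protocol and SAP*

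**What the plan says.** **Masking.** Section 6.0, Blinding, keeps families masked to the study arms by presenting the study at consent as one of technology-based interventions for pain. The form is not to give specific detail on VR-BF or Manage My Pain "or indicate the use of any device, such as a headset". Disclosure comes later: "Once assigned to a group, patients will receive a handout describing the intervention with instructions and information about what participation entails".

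**Consent content.** Section 13.0, Requirements: "The consent form will describe the purpose of the study, the procedures to be followed, and the risks and benefits of participation". Section 22.0 repeats that the form covers "the procedures to be followed, and the risks/benefits of participation".

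**Risks.** Section 15.0 describes study risks as minimal or absent, "with the greatest risk being motion sickness while the headset is in place", and adds "a theoretical risk of inducing seizures (0.025% in pediatric data supplied by a similar Samsung device"). Both arise from wearing the headset.

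**Feasibility measures.** Section 6.0, Data Collection, defines enrollment and randomization as agreeing to take part and being willing to be randomized, and retention as taking part in the last study visit. Each has an 80% benchmark. Table 3 also collects "Reasons for refusal, including unwillingness to be randomized". Section 17.0 assesses the measures for each arm and asks whether 80% lies inside a two-sided 95% confidence interval.

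**The concern.** A form that describes the VR-BF procedures and the headset's risks will indicate a device. A form that indicates no device cannot fully describe the procedures. Staff are left to choose, and different recruiters may choose differently, so families may be told different things before agreeing. Participants are aged 12 to 18, and much of the use is independent home practice.

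There is also a measurement problem in Aim 2. Agreement is counted before the family learns which technologies are involved. A family that would decline a headset can then be counted as an enrollment success and, if assigned to VR-BF, later as a retention or adherence failure. The pilot exists to inform an efficacy trial and to show that both arms are feasible, so it matters at which step such a refusal is recorded. The plan does not say.

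**Working it through.** **1. The sections side by side**

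| Point | Section | Content |
|---|---|---|
| What consent omits | 6.0, Blinding | Specific detail on either intervention; any device |
| What consent contains | 13.0 and 22.0 | Purpose, procedures, risks, benefits |
| Main risks | 15.0 | Motion sickness; theoretical seizure risk taken from a similar device |
| Exception for Aim 1 | none | All 12 to 32 Aim 1 patients receive the headset |
| Rule for refusal after the handout | none | Reasons for dropout and for non-adherence are collected |

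The risk requirement could be met by naming symptoms without naming a device. The procedures requirement could not be met in full, because the VR-BF procedure consists of using the device.

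**2. Disclosure elsewhere before use**

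- Section 13.0: staff describe procedures and verify eligibility before consent.
- Section 10.0: the criteria refer to motion sickness, seizure disorder and ability to use the VR headset.
- Section 6.0, VR session: the tutorial tells patients to remove the device for motion sickness, dizziness or nausea. Seizure is not mentioned.
- Section 6.0, Device Tracking: families receiving the headset are asked to sign a Device Agreement. Its stated purpose is retrieval of equipment.

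The handout is described as covering the intervention, instructions and what participation involves. Risks are not listed.

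**3. The plan's own figure**

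Section 17.0 plans 70 patients, 56 analyzed, for an exact 95% interval of width 0.22 at 80%. At n = 56 the Clopper-Pearson interval at 80% is 67.2% to 89.5%, width 0.223, and 56/0.80 = 70. The figure reproduces, but it does not bear on the conflict. Per arm, 28/35 gives 63.1% to 91.6%, width 0.285.

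**4. Possible effect on VR-BF retention**

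Let r be the share of enrolled families who would refuse the headset once told. The documents give no value, so r is assumed. Assume also that other retention is 80% and that each refuser misses the last visit.

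VR-BF retention = 0.80 × (1 − r). The exact interval for n = 35 lies wholly below 80% when 22 or fewer are retained (22/35: 44.9% to 78.5%; 23/35 has an upper limit of 80.9%).

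| r (assumed) | VR-BF retention | Expected retained of 35 | Chance the interval lies wholly below 80% |
|---|---|---|---|
| 0% | 80% | 28.0 | 1% |
| 5% | 76% | 26.6 | 6% |
| 10% | 72% | 25.2 | 15% |
| 20% | 64% | 22.4 | 51% |

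An observed 25/35 gives 53.7% to 85.4%, which contains 80%.

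**5. Possible effect on enrollment**

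Assume 85% agree under masked consent. Enrolling 70 then needs about 70/0.85 = 82 approached. With r = 10% and full disclosure beforehand, agreement would be 0.85 × 0.90 = 76.5%, or about 63/82. The exact interval is 66.2% to 85.4%, which also contains 80%.

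**The case against.** The strongest reply is that the protocol may work in practice. The Blinding paragraph withholds specific detail and device use, but does not forbid listing motion sickness as a risk. The conversation before consent, the eligibility questions, the tutorial and the signed Device Agreement all bring the headset or its effects into view before home use. Reasons for dropout and non-adherence are collected, measures are reported by arm, and a CONSORT diagram is planned, so headset refusals could often be traced.

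Much of this stands, and it limits what can be claimed. Three stronger readings might be inferred, and the documents do not support them.

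- *Families consent without knowing the headset risks.* The consent form was not available, and the disclosures above are partial but real.
- *Enrollment is biased up and VR-BF retention down, with nothing comparable in control.* The app is masked too, so control families may also leave once they learn what they received. The net difference between arms is unknown. If the efficacy trial keeps the same masked consent, the masked rates are also the ones it will see.
- *The verdict against 80% flips.* Under the Section 17.0 rule, the illustrative intervals for 63/82 and 25/35 both contain 80%. A flip appears only if point estimates are read against Table 3, and then only with assumed inputs.

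The reply leaves two gaps. If staff disclose the headset before consent, the masking intended by the Blinding paragraph is lost; if they do not, full description of procedures is missing. Masking to arms also gives no reason to withhold the device in Aim 1.

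**Conclusion.** The instructions conflict as written and must be reconciled; this rests on the text alone. The effect on the feasibility measures is conditional. A family unwilling to use a headset may be counted as enrolled and then as VR-BF loss or non-adherence, and no rule says how to classify it.

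The size cannot be computed from the documents. With other retention at 80% and every refuser missing the last visit, an assumed 5% to 10% refusal lowers VR-BF retention by 4 to 8 points. The planned interval check would flag that in only about 6% to 15% of trials. This is a correction worth making, not evidence that the design fails.

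**What to change.** Reconcile the Blinding paragraph of Section 6.0 with Sections 13.0, 15.0 and 22.0.

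1. **Aim 1:** describe the headset and its risks in the consent. There are no arms to mask.
2. **Aim 2:** state in the consent that a technology under study may cause the risks named in the protocol, without saying which arm is experimental. Give the full procedures and risks in the post-assignment handout, and record agreement or refusal before first use, in both arms.
3. **Counting:** show refusals at that step by arm as a separate CONSORT line, and report enrollment and retention with and without them. At the assumed r = 10%, VR-BF retention would read 25.2/35 = 72% with all randomized patients and 25.2/31.5 = 80% among those who accepted, which separates unwillingness to use a headset from later dropout. Enrollment less these refusals is only a partial correction, because only VR-BF families are offered the headset.

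The cost is an IRB amendment to the consent and handout (two consent versions if one form now serves both aims), one recorded item per patient and one CONSORT line. Families may guess that a device is involved, and enrollment may be slightly lower. Masking to which arm is experimental is kept.

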sampling will be used to select a representative patient group according to age, sex, and race. We anticipate recruiting about 1 patient per week. Patients will be identified when scheduled for surgery. They will receive scripted instruction on the Oculus/Meta Quest and a tutorial on the biofeedback application. Once device and content education are complete, patients will receive manual-based training on the benefits of HRV BF.⁵⁶ They will be given the appropriate equipment and instructed to complete an independent daily, 10-minute session (based on the standard duration of a BF session) and record each session in a log. Patients will bring the equipment to the hospital on the day of surgery for continuation into Aim 1b. After surgery, patients will have free use of VR-BF. They will be instructed to undergo, at minimum, one daily, 10-minute session. They will also be instructed to freely use VR-BF, particularly when in pain. They will use a log to record their VR-BF usage (date, time, and duration). Patients will be visited daily, or more or less frequently as applicable/needed, to assist with log completion and any issues. On the day of discharge, a study team member will conduct a detailed, semi-structured interview. Patients may take the VR-BF device home for up to two weeks for home pain management; a similar log will be used to document home use. We will enroll 4 patients at a time and analyze data to refine the protocol in an iterative fashion; this process will be repeated until 12 patients are enrolled. If further data is required for protocol refinement, we will continue recruiting patients in groups of 4 as necessary until a maximum number of 32 patients is reached.

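### Aim 2 schedules postoperative anxiety ratings only around sessions, so the by-arm anxiety description depends on who used the intervention and when

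*Combined protocol and SAP*

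**What the plan says.** The Aim 2 research design in Section 6.0 ties anxiety to sessions: "patients will also be asked to document pain and anxiety scores before and after each VR-BF or application session using the NRS". The time points follow: "Patients will self-report and document these scores before each session and then immediately, 15 minutes, and 30 minutes after session completion". Nursing records are ruled out as a second source: "anxiety scores are not documented by the nursing staff so only self-reported scores will be used". The Additional Data Collection part of Section 6.0 repeats the timing: "Anxiety and pain will be collected with numerical rating scale (NRS) prior to and after the VR intervention for patients in all 3 cohorts".

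Pain scores and opioid consumption are handled differently. They "will be collected from EPIC, the electronic medical record, for each 24-hour period during study enrollment", whether or not a session took place. For the optional period at home, "patients will complete a daily log/report documenting use, pain scores, and opioid consumption"; anxiety is not in that list.

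Section 17.0 (Aim 2, feasibility analysis) describes pain, anxiety and opioid use by treatment arm without testing. It gives no summary unit and no rule for patients or days without scores. Sections 1.0 and 17.0 name anxiety among the outcomes to be carried into the efficacy trial.

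**The concern.** Whether anxiety is observed depends on using the assigned intervention. Adherence is itself a feasibility outcome with an 80% target, so incomplete use is expected. The arms also ask different things of the patient: a headset, chest strap and ear clip in one, an app in the other. Unequal use is therefore plausible.

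If use is related to anxiety, a by-arm anxiety summary partly reflects who used the intervention and on which days. A difference in use between arms could then look like a difference in anxiety. Session timing is also largely the patient's choice. The Aim 1 text says of postoperative use: "They will also be instructed to freely use VR-BF, particularly when in pain".

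What is at stake is the preliminary anxiety estimate handed to the efficacy trial. Ratings not taken on days without sessions cannot be recovered by later analysis.

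**Working it through.** The plan gives no figure for anxiety completeness, so there is none to reproduce. The check has two parts.

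**1. Sources set side by side (Aim 2, after surgery)**

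- Pain: medical record for every 24-hour period, plus session self-reports, plus the home log if chosen.
- Opioid use: medical record for every 24-hour period, plus the home log if chosen.
- Anxiety: session self-reports only. The coordinator (CRC) visits carry no anxiety rating. The case report form list in Section 6.0 includes "b) anxiety and pain scores", but as data that may be collected, with no time point.

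Of the three outcomes, only anxiety has no scheduled inpatient source that is independent of use.

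**2. Size under stated assumptions**

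From the documents: SD of baseline anxiety 2.50 in the VR-BF pilot (Section 3.0, Table 1). Assumed: no true effect; one arm split at the median of anxiety; use on 90% of days in the less anxious half and 50% in the more anxious half; use unrelated to anxiety in the other arm; each patient's anxiety stable over the stay; normal distribution, so the half means lie 0.798 SD below and above the arm mean.

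If the two halves contribute with weights w1 (less anxious) and w2 (more anxious), the bias in the arm mean is 0.798 × (w2 − w1)/(w1 + w2) × 2.50.

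*Patient-days pooled.* The weights are the shares of days used.

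- 90%/50%: 0.798 × (0.5 − 0.9)/1.4 = −0.228 SD; × 2.50 = −0.57 points.
- 80%/60%: 0.798 × (0.6 − 0.8)/1.4 = −0.114 SD; × 2.50 = −0.28 points.

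*One mean per patient.* Only patients with no session drop out. With independent days over a stay of D days, the weights are 1 − (1 − p)^D. Length of stay is not given beyond at least one night, so D is assumed. For D = 3:

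- 90%/50%: weights 0.999 and 0.875; 0.798 × (−0.124)/1.874 = −0.053 SD; × 2.50 = −0.13 points.
- 80%/60%: weights 0.992 and 0.936; 0.798 × (−0.056)/1.928 = −0.023 SD; × 2.50 = −0.06 points.

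The same formula gives −0.28 and −0.13 points for D = 2, and −0.03 and −0.01 for D = 5.

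*Shape of the scale.* A mean of 2.05 with SD 2.50 on 0-10 is skewed. Matching a beta distribution on 0-10 to those moments changes the pooled figures to −0.52 and −0.26; a gamma gives −0.46 and −0.23. The normal approximation overstates somewhat but does not change the picture.

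*Second route, zero-session patients only.* If a share u of an arm has no session and these patients differ from users by d points, the users-only mean is off by u × d. With d from 1 to 3 (assumed), that is 0.1 to 0.3 points at u = 10% and 0.2 to 0.6 at u = 20%. Of 35 patients per arm, 31.5 and 28 would then contribute. The 80% adherence target does not fix u, because a non-adherent patient may still complete some sessions.

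*For scale.* With 28 patients, the 95% half-width for a mean with SD 2.50 is 1.96 × 2.50/√28 = 0.93 points.

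**The case against.** The case for leaving the plan alone has several parts.

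- Anxiety is exploratory and untested, and no benchmark or sample size rests on it. This stands.
- Section 17.0 does not say that patient-days will be pooled. The nearest stated rule, in the exploratory dose analysis that is repeated for anxiety, takes a mean for each patient. On that basis the illustrated bias falls to about 0.13 points over 3 days. This stands, although that calculation assumes stable anxiety and so leaves out patients choosing when to rate themselves.
- The scenario puts selection in one arm only. Controls are meant to use the app in a parallel way, and nothing in the documents supports that asymmetry. This stands; it is an illustration.
- The sign is open. Less use by anxious patients lowers the observed level; use at distressed moments raises it. The instruction to use VR-BF when in pain is also Aim 1 text, and the Aim 2 regimen follows the protocol refined in Phase 1.
- Use is recorded in both arms with reasons for failure, so unequal use would be visible. That helps interpretation but supplies no missing ratings.
- The questionnaires, the interview guide and the design figure are not in the text available. An anxiety item there cannot be excluded, but the questionnaire and interview are described as feedback on the patient's experience at the final visit, not daily ratings.

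A reader might infer that anyone who skips or stops has no anxiety data at all. The schedule does not support that: earlier session scores remain, and only a patient with no sessions has none. A reader might also set 0.57 against the pilot's immediate fall of about 0.9 points and conclude that much of a VR-BF effect could be spurious. That does not follow. The 0.9 is a before/after change within a session, whereas the bias here is in an arm's level. Nor do the pilot's reasons for declining (tiredness, pain) show anxiety-related skipping; they concern enrolment after surgery, and the plan already responded by recruiting before it.

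**Conclusion.** The gap is real but modest in consequence. As scheduled, postoperative anxiety in Aim 2 is observed only around use of the assigned intervention, so the by-arm description mixes anxiety with who used it and when. The documents give neither patterns of use nor a summary unit, so no single size can be stated. Under the 90%/50% one-arm scenario the bias is about 0.57 points with pooled patient-days and about 0.13 with one mean per patient over an assumed 3-day stay. Milder selection or a longer stay gives less. The direction is unknown, and the documents do not support a claim that VR-BF would be favoured. The feasibility endpoints, the sample size of 70 and the within-session before/after analysis are not affected. This is a cheap improvement to the data passed on to the efficacy trial.

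**What to change.** In Section 6.0 (Aim 2), add one NRS anxiety rating at a fixed time on each postoperative hospital day, for every randomised patient in both arms, whether or not a session was done. Take it at the coordinator visit, or in REDCap when there is no visit.

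In Section 17.0, name this rating as the basis of the by-arm anxiety description, and report how many patients and days contribute in each arm. Keep the session scores for the before/after analysis in the exploratory dosing section.

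The cost is one 0-10 question per hospital day, mostly at a contact already planned, with slightly more patient burden. No treatment, endpoint or sample size changes.
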